6.4 Drug Storage and Accountability

SHR0302 must be stored according to the labeled storage conditions in a locked area with restricted access. The investigator or appropriate delegate at the site (e.g., pharmacist), will ensure that all study drug is stored in a secured area, under recommended storage condition, and in accordance with regulatory requirements.

The investigator must maintain adequate records documenting the receipt, use, loss, or other disposition of the investigational product(s). To ensure adequate records, all drug supplies will be accounted for in the drug accountability inventory forms as instructed by Reistone Biopharma/designated CRO and will be monitored by counting of unused medications returned by the subject at Week 4, 8, 12 of the treatment period or at follow-up (if the subject withdraws).

At the end of trial, Reistone Biopharma/designated CRO will provide instructions as to the disposition of any unused investigational product. If Reistone/designated CRO authorizes destruction at the trial site, the investigator must ensure that the materials are destroyed in compliance with applicable environmental regulations, institutional policy, and any special instructions provided by Reistone Biopharma/designated CRO. Destruction must be adequately documented. SHR0302 will not be made available to subjects at the end of study.

6.5 Treatment Compliance

Investigational product compliance will be assessed by the study center at each clinic visit following baseline (Day 0) up to the end of treatment. Non-compliance is defined as taking less than 80% of study drug products as directed by the dosing instructions. The investigator has the discretion to withdraw any subject from the study for reasons of non-compliance with the dosing regimen. Investigators should indicate on the appropriate eCRF page noncompliance with study treatment and provide an explanation.

Inventory control of all study medications must be rigorously maintained throughout the duration of the study until all medication has been accounted for and returned to the sponsor. Any discrepancies noted between drug dispensing records and the drug inventory must be reported to Reistone Biopharma/designated CRO.

Previous treatment

All treatment for atopic dermatitis including systemic steroids after the first diagnosis of atopic dermatitis (as determined by medical history or by medical inquiry) and all treatment performed within 4 weeks prior to screening must be documented in the eCRF. Reasons for discontinuing these medications should be recorded as:

- Never achieved a satisfactory response
- A satisfactory response was initially achieved, but later became ineffective
- Treatment discontinuation due to intolerance/side effects
- Other (detailed description)

6.6 Concomitant Medications

6.6.1 Permitted Concomitant Medications

All concomitant medication(s) taken during the trial must be recorded with indication, daily dose, and start and stop dates of administration. At screen visit (Visit 1), subjects will be provided with non-medicated study emollient. Subjects will start the emollient twice daily 2 weeks prior to the baseline visit (Visit 2). The non-medicated study emollient is the only topical products permitted to be used on atopic dermatitis skin during the study. If a subject has a history of intolerability or currently does not tolerate the non-medicated study emollient, the investigator should contact Reistone for approval to use an alternative topical treatment; the approved alternative non-medicated emollient should be documented in study records.

At the same time, all subjects will also be asked about other co-medications at each clinic visit and recorded in the co-medications section of the CRF. Other concomitant medications allowed if needed during the study are as follows:

- o Over-the-counter shower gel
- o Oral antihistamines
- Nonsteroidal anti-inflammatory drugs

In addition, the investigator or appropriate study staff should be consulted before the subject starts a new combined treatment regimen during the study.

6.6.2 Prohibited Medications

The following medications are prohibited throughout the duration of the study:

- o Topical treatment for AD (including but not limited to topical corticosteroids, calcineurin inhibitor, herbal, etc.)
- Phototherapy
- O Cyclosporin and other immunosuppressant (e.g., methotrexate, mycophenolate mofetil and azathioprine, etc.)
- o Systemic corticosteroids
- o Biologics

In addition, concomitant administration of CYP3A inducers and moderate to potent CYP3A inhibitors with systemic effects should be avoided during the study.

Examples of medications that are prohibited from use from 28 days prior to the first dose of study medication until completion of follow up period, due to potential for drug interactions or confounding of data interpretation, are listed in Appendix 4.

All live vaccines immunization are prohibited from signing of informed consent, throughout the duration of the study, and for 1 month after lase dose of study medication.

6.6.3 Prohibited Medications Washout

Subjects who have received systemic corticosteroids, cyclosporin and other immunosuppressant (e.g., methotrexate, mycophenolate mofetil and azathioprine, etc.) \ PDE4 inhibitor as well as phototherapy treatment should washout at least 4 weeks prior to first dose of study drug. Subjects who have topical treatment for AD (e.g., topical corticosteroids, calcineurin inhibitor and herbal, etc.) should washout at least 2 weeks prior to first dose of study drug.

6.6.4 Traditional Chinese Medicine and Herbal Medicines

The following categories of traditional Chinese medicine or herbal medicine are prohibited during the study:

- o Traditional Chinese medicine or herbal medicine used for the treatment of AD, including those which may contain corticosteroids according to investigator's judgment.
- o Traditional Chinese medicine or herbal medicine known effects on platelets and that increase bleeding tendency.

6.7 Treatment after study completion

The investigator is responsible for ensuring that consideration has been given to the post-study care of the patient's medical condition whether nor not Reistione Biopharma/designated CRO is providing specific post study treatment after week 12. Reistione Biopharma/designated CRO has provided a 12-week double-blind treatment period and will not provide treatment after the end of the 12-week treatment period. Post-treatment AD therapy should not be entered into the eCRF.

6.8 Study Drug Overdose Management

An overdose is defined as a dose greater than the total doses described above which results in clinical signs and symptoms. These should be recorded by the investigator on the AE/SAE pages. In the event of an overdose of study medication, the investigator should use clinical judgment in treating the overdose and contact the study medical monitor.

Reistone Biopharma/designated CRO is not recommending specific treatment guidelines for overdose and toxicity management. The investigator is advised to refer to the relevant document(s) for detailed information regarding warnings, precautions, contraindications, adverse events, and other significant data pertaining to the study drug being used in this study. Such documents may include, but not be limited to, the IB or equivalent document provided by Reistone Biopharma/designated CRO.

7. Study Assessments and Procedures

7.1 Critical Baseline Assessments

The following key baseline assessments will be performed at Visit 1:

- Demographic history (including gender, ethnic origin, date of birth, height, and weight)
- Medical history of atopic dermatitis, including date of diagnosis (year of diagnosis is acceptable) and previous and/or current medical conditions
- Physical examination
- Heart rate, blood pressure, respiratory rate and temperature measurement
- 12-lead ECG
- Chest X-ray (or previous CT scan results obtained within 3 months of Screening (Visit 1))
- Clinical laboratory evaluation (including biochemistry, hematology, urine pregnancy test)
- IGA (Investigator's Global Assessment)
- EASI (Eczema Area and Severity Index)
- SCORAD (Scoring Atopic Dermatitis)
- Pruritus numerical rating scale (NRS)
- Dermatology Life Quality Index (DLQI)

7.2 Efficacy Endpoint Assessment

7.2.1 Investigator's Global Score (IGA)

Primary Efficacy Endpoint: the treatment response rate based on Investigator's Global Assessment (IGA). The IGA score is a very simple and convenient assessment method, which is commonly used in clinical research as a gold-standard clinical assessment tool¹⁴. The IGA score will be assessed at each visit by the investigator using clinical characteristics of erythema, infiltration, papulation, oozing, and crusting as guidelines for the overall severity assessment. The IGA consists of a 6-point severity scale from clear to very severe disease (See Table 3). The assessment will be static evaluation without regards to the score at a previous visit.

Table 3. Investigator's Global Score (IGA)
--

Score	Category	Description
0	Clear	Atopic dermatitis is cleared, except for any residual
		discoloration
1	Almost clear	Only just perceptible erythema and perceptible
		papules/infiltrates or edema
2	Mild	Mild erythema, and mild papules/infiltrates or edema
3	Moderate	Moderate erythema, and moderate papules/infiltrates or edema
4	Severe	Severe erythema, and severe papules/infiltrates or edema
5	Very Severe	Very severe skin lesions, severe erythema, and severe
		papules/infiltrates or edema with exudation/crusting.

7.2.2 Eczema Area and Severity Index (EASI)

The EASI score is the sum of the skin lesion severity scores and the integral and coefficient product of the area affected by the skin lesions in the four parts of the body: head and neck, trunk, upper limbs, and lower limbs. The specific calculation methods are as follows: ① The clinical manifestations of the severity of skin lesions are divided into four items, namely erythema (E), infiltration (edema) or papules (induration (edema)/papulation, I), epidermal exfoliation (excoriation, Ex), lichenification (lichenification, L). The severity of each clinical manifestation was scored on a 0-3 scale: 0 = none, 1 = mild, 2 = moderate, and 3 = severe (for details see Table 4). Half of the scores, and 0. 5, can be recorded between symptom scores. ② Lesion area size score: The whole body was divided into four parts, namely, head and neck (H), trunk (T), upper limb (UL), lower limb (LL). Using the patient's palm as an estimate of 1%, the four-part lesion area was converted into a proportion of the site scored on a scale of 0 to 6: 0 for no rash, 1 for < 10%, 2 for 10% to 29%, 3 for 30% to 49%, 4 for 50% to 69%, 5 for 70% to 89%, and 6 for 90%

to 100%. 3 Then according to the proportion of body parts in the whole body (see details Table 5), each part was multiplied by the corresponding percentage coefficient, and the score of each part was added as the total score of EASI skin lesion symptom severity, which was calculated by the following formula, and the total score was 0-72 ¹⁵.

EASI = 0.1Ah (Eh + Ih + Exh + Lh) + 0.2Au (Eu + Iu + ExU + Lu) + 0.3At (Et + It + Ext + Lt) + 0.4Al (El + Il + Exl + Ll)

A = area score; E = erythema; I = infiltration/papulation; Ex = excoriation; L = lichenification; H = head/neck; U = upper limbs; T = trunk; L = lower limbs.

The EASI score ranges from 0.0 to 72.0, can be varied in increments of 0.1, Higher scores indicate greater severity.

Table 4. Clinical severity scoring criteria for the Eczema Area and Severity Index (EASI)

Erythen 0 1 2	Absent Mild	None; may have residual discoloration
1		
	Mild	T' 1, ' 1, 1' 1, 1
2		Light pink to light red
	Moderate	Red
3	Severe	Deep, dark red
Infiltrat	ion/Papulation(I	
0	Absent	None
1	Mild	Barely palpable to slight, but definite hard thickened skin and/or papules
2	Moderate	Easily palpable moderate hard thickened skin and/or papules
3	Severe	Severe hard thickened skin and/or papules
Excoria	tion (Ex)	
0	Absent	None
1	Mild	Slight, but definite linear or picked scratch marks or penetrating surface injur
2	Moderate	Moderate linear or picked scratch marks or penetrating surface injury
3	Severe	Severe linear or picked scratch marks or penetrating surface injury

0	Absent	None
1	Mild	Barely perceptible to slight, but definite thickened skin, fine skin markings and lichenoid scal
2	Moderate	Moderate thickened skin, coarse skin markings, and coarse lichenoid scale
3	Severe	Severe thickened skin with very coarse skin markings and lichenoid scale

Table 5. Body Region Surface Area (BSA)

Body region	The proportion of each part
Head/neck	0.1
Upper limbs	0.2
Trunk	0.3
Lower limb	0.4

7.2.3 Atopic Dermatitis Score (SCORAD)

SCORAD is a scoring standard proposed by the European Atopic Dermatitis Research Group (ETFAD) in 1993. It integrates the observational assessment of physicians and patients and is recognized by the Harmonizing Outcome Measures for Eczema (HOME) as an effective assessment method that can be used in clinical research and clinical practice ¹⁴.

The scoring scale consists of three major sections: the objective signs section includes lesion area (A) and lesion severity (B), and the subjective symptoms include the degree of itching and sleep effects (C), as detailed in Appendix 5.

- A. Lesion area: In adults, the lesion area was estimated according to the "rule of nine": head and neck 9%, double upper limbs 18%, trunk back 36%, lower limbs 36%, perineum 1%. Taking 1% of the area as 1 point, the total area score is A (maximum score 100).
- B. Lesion severity: Overall assessment of six clinical features including erythema, papular (or) edema, exudation (or) crusting, epidermal exfoliation, lichenification, and dry skin (uninvolved skin only). According to the severity of skin lesions, each item was rated as 0-3 points on a four-grade scale, and six parts were summed as B (maximum score 18).
- C. Itching and sleeplessness: The evaluation was performed using a visual analogue scale (VAS) method, with 0-10 points for each item (itching 0 = no itching, itching 10 = very itchy; sleep 0 = no impact, sleep 10 = severely affected), taking the sum of the mean scores of itch and sleep impact in the last 3 days as C (maximum score 20).

SCORAD total score = A/5 + 7B/2 + C with a score of 0-103.

7.2.4 Pruritus Numeric Rating Scale (NRS)

Pruritus Rating: At each visit, the degree of pruritus/scratching was assessed by the subject on an 11-grade rating scale from 0 (no pruritus/scratching) - 10 (severe pruritus/scratching) for the first 24 h of the visit (see details in Appendix 5).

7.2.5 Skin Disease Quality of Life Index (DLQI)

The DLQI is a commonly used dermatology-related questionnaire that allows subjects to assess the impact of skin disease on quality of life through 10 questions (see details in Appendix 6), widely used in clinical studies of AD.

Subjects should complete questionnaires prior to all other study-related procedures at each visit. The DLQI questionnaire will be checked by the study center staff before the subject leaves the study center. All completed DLQI questionnaires will have CRA returned and sent to the sponsor for transcription into the EDC system.

7.3 Safety assessment

7.3.1 Vital Signs

Vital signs measurements will include heart rate as well as systolic and diastolic blood pressure and body temperature, and height and weight. Vital signs will be obtained after subjects have rested for approximately 5 minutes and before performing ECG. A sigle set of values will be collected.

Vital signs will be performed using equipment provided by sites and will be obtained at visits and time points as detailed in Section 5.11 - Time and Event Tables.

7.3.2 12-lead ECG

12-lead ECG measurement and rhythm strip (10 seconds) will be obtained after measurement of vital signs. Triplicate ECG measurements are collected at rate of 3 ECGs over 5 minutes period. After vital signs are obtained subjects should be placed in the supine position for the ECG measurements.

ECG measurements will be taken at various visits and time points as detailed in Section 5.11 – Time and Event Table. The investigator, a designated sub-investigator, or other appropriately trained site personnel will be responsible for performing 12-lead ECG assessments. The investigator must provide his/her dated signature on the original paper tracing, attesting to the authenticity of the ECG machine interpretation. The investigator will review the ECG and determine if the subject should continue the study.

7.3.3 QuantiFERON-TB Gold Test

QuantiFERON-TB Gold ® TM test may be used at the discretion of the investigator based on the implement ability of the local test. The mechanism of QuantiFERON-TB Gold Test is that this enzyme-linked immunosorbent assay (ELISA) assay detects interferon-gamma (IFN-γ) release in

sensitized humans when fresh heparinized whole blood is co-incubated with a synthetic peptide mixture mimicking two proteins in M. tuberculosis, early secretory antigen target protein-6 (ESAT-6) and culture filtrate protein-10 (CFP-10). ESAT-6 and CFP-10 are secreted by all M. tuberculosis and pathogenic M. bovis strains. Since all Bacillus Calmette-Guérin (BCG) vaccine strains and common non-tuberculous mycobacteria (except M. kansasii, M. stephensi and M.mainum) neither of these proteins are present, so the QuantiFERON-TB Gold assay is more specific for M. tuberculosis than the test in which tuberculin purified protein derivative (PPD) is used as antigen.

7.3.5 T-SPOT.TB test

T-SPOT may be used at the discretion of the investigator based on the implement ability of the local test. The mechanism of T-SPOT TB assay is that tuberculosis-specific antigen stimulation of activated effector T cells (secreting gamma interferon) can be detected by this enzyme-linked immunospot (ELISPOT) assay when peripheral blood mononuclear cells are co-incubated with a synthetic peptide mixture mimicking both proteins in M. tuberculosis (early secretory antigen target protein-6 (ESAT-6) and culture filtrate protein-10 (CFP-10)). Each spot represents a gamma interferon-secreting T cell, and the number of spots is counted to obtain the number of tuberculosis-primed T cells in the peripheral blood. Similar to the QuantiFERON-TB Gold assay, compared to the PPD assay, T-SPOT.TB test is more specific for M. tuberculosis.

7.3.5 Clinical Laboratory Testing

Routine, non-fasting clinical laboratory (hematology and chemistry and urinalysis) tests will be performed as detailed in Section 5.11 – Time and Event Table. At the discretion of the investigator, additional samples may be taken for safety reasons. All blood samples will be measured at a designated central laboratory.

A urine pregnancy test will be performed for all females of childbearing potential as detailed in Table 6.

The study clinical laboratory tests including analytes for clinical chemistry and hematology are shown below in Table 6.

Table 6. Clinical Laboratory Testing Lists

Biochemistry	Hematology	Urinalysis	Other
Albumin	Hemoglobin	рН	Hepatitis B surface antigen ¹
Alkaline phosphatase	Hematocrit	Protein	Hepatitis C virus antibody ¹
Alanine aminotransferase (ALT or SGPT)	Platelet count	Glucose	HIV tests ¹
Aspartate aminotransferase (AST or SGOT)	WBC count	Bilirubin and White Cell Count	Urine pregnancy test (performed in clinic) ²
Bilirubin, direct	RBC count		FSH ³
Bilirubin, indirect	Neutrophils, absolute		β-HCG blood test ⁴
Bilirubin, total	Neutrophils, segs (%)		Lipid check item (fasting) total cholesterol, low density lipoprotein (LDL) high density lipoprotein (HDL) triglyceride
Calcium	Neutrophils, bands (%)		Thyroid function tests, including TSH, free T4, and free T3
Chloride	Basophils (%)		total IgE
CO2 content/Bicarbonate	Eosinophils (%)		PK sampling ⁵
Creatinine	Eosinophils, absolute		
Creatine phosphokinase (CPK), total	Lymphocytes (%)		
Gamma glutamyl transferase (GGT)	Monocytes (%)		
Glucose			
Phosphorus			
Potassium			
Protein, total serum			
Sodium			
Urea nitrogen (BUN)			
Uric Acid			

- 1 Assessed at Visit 1 (Screening) only
- 2 All visits subsequent to the screening visit
- 3 FSH for confirmation of postmenopausal status at screening visit only
- 4 Only for females of child-bearing potential at screening, and if urine pregnancy test positive
- 5 Only done as per Section 7.4 Pharmacokinetics

7.3.6 Immunoglobulin E (IgE)

Atopic dermatitis is divided into endogenous and exogenous types. In adult AD patients, exogenous AD accounts for approximately 80% and endogenous AD for 20%. Patients with exogenous AD usually present with elevated serum total IgE ¹⁶. Blood samples will be collected for detection of IgE levels at screening, baseline, week 1, week 4, week 8, and week 12.

7.3.7 Lipid Profile Testing

A fasting lipid profile blood collection, as per Section 5.11 – Time and Event table, will require subjects to refrain from all food and liquids (water and non-study medications permitted) for at least 10 hours prior to scheduled laboratory tests.

7.3.8 Liver Biochemistry – Stopping and Follow-up Criteria

Phase II Liver Biochemistry Stopping and Follow-up Criteria have been designed to ensure subject safety and to assess liver event etiology (consistent with FDA premarketing clinical liver safety guidance). If any of the following conditions occur at any time during the study drug treatment period, the study drug should be discontinued immediately with appropriate clinical follow-up (including repeat laboratory tests until the subject's laboratory values return to normal or return to baseline condition):

- ALT or AST > 8 x ULN, or
- ALT or AST > 5 x ULN and retest 5 x ULN, or
- ALT or AST > 3 x ULN with elevated total bilirubin > 2 x ULN, or international normalized ratio > 1.5, or
- ALT or AST > 3 x ULN associated with fatigue, nausea, vomiting, right upper quadrant pain or tenderness, fever, rash.

For one of above criteria, make every effort to carry out the liver event follow-up assessment of described below:

- Viral hepatitis serology including:
 - Hepatitis A IgM antibody;
 - Hepatitis B surface antigen and Hepatitis B core antibody (IgM);
 - Hepatitis C virus RNA;
 - Cytomegalovirus IgM antibody;
 - Epstein-Barr viral capsid antigen IgM antibody (if not available, obtain heterophile antibody or monospot testing);
 - Hepatitis E IgM antibody
- Blood sample for pharmacokinetic (PK) analysis, obtained within 24 hours of last dose. Record the date/time of the PK blood sample draw and the date/time of the last dose of investigational product prior to blood sample draw on the eCRF. If the date or time of the last dose is unclear, provide the subject's best approximation. If the date/time of the last dose cannot be approximated OR a PK sample cannot be collected in the time period indicated above, do not obtain a PK sample. Instructions for sample handling and shipping are in the SPM.
- Serum creatine phosphokinase (CPK) and lactate dehydrogenase (LDH)

- Fractionate bilirubin, if total bilirubin≥2xULN
- Obtain complete blood count with differential to assess eosinophilia
- Record the appearance or worsening of clinical symptoms of hepatitis, or hypersensitivity, such as fatigue, nausea, vomiting, right upper quadrant pain or tenderness, fever rash or eosinophilia as relevant on the AE report form
- Record use of concomitant medications, acetaminophen, herbal remedies, other over the counter medications, or putative hepatotoxins, on the concomitant medications report form
- Record alcohol use on the liver event alcohol intake eCRF

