5.9 Stopping Criteria

The stopping safety criteria are as follows:

- Liver chemistry threshold stopping criteria have been designed to assure subject safety and to evaluate liver event etiology (in alignment with the FDA premarketing clinical liver safety guidance). Study treatment will be stopped if the liver chemistry stopping criteria is met. Refer to Section 7.3.8 Liver Chemistry Stopping and Follow-up Criteria.
- Subject that meets the QTc criteria below will be withdrawn from the study. The QT correction formula used to determine discontinuation should be the same one used throughout the study.
 - QTc, QTcB/QTcF > 500ms
 - Change from baseline: QTc > 60ms

Withdrawal decisions are to be based on an average QTc value of triplicate ECGs. If an ECG demonstrates a prolonged QT interval, obtain 2 more ECGs over a brief period, and then use the averaged QTc values of the 3 ECGs to determine whether the subject should be discontinued from the study.

- An unacceptable adverse event, as determined by the Investigator and the medical monitor
- Any unacceptable adverse event that is thought to be related to the investigational product may result in the study being terminated
- Significant protocol deviation. The discovery that post-randomization the subject failed to meet protocol entry criteria or did not adhere to protocol requirements, and continued participation poses an unacceptable risk to the subject's health
- If the subject is found to be pregnant, the subject should be withdrawn immediately. The procedure is detailed in Section 7.3.10

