5.11 Time and Event Tables

See details in Table 1.

Table 1. Time and Event Table

Period	Screening	Baseline	Treatment period			Follow-up/ EW ¹²	
Visit	1	2	3	4	5	6	7
Study Week	-4 to -1	0	1	4	8	12	14
Study Day	-28to -1	0	7 ± 2 days	28 ± 3 days	56 ± 3 days	84 ± 3 days	98 ± 3 days
Procedures		•					
Written Informed Consent ¹	X						
Demography/Medical History ²	X						
Physical Examination	X	X	X	X	X	X	X
Height	X						
Weight	X						X
Chest X-ray ³	X						
Inclusion/Exclusion Criteria	X						
Randomization criteria		X					
Study Drug Dispensing		X		X	X		
Study Drug Accountability				X	X	X	x 13
Enrollment Visit in IVRS ⁴	X	X	X	X	X	X	x 13
Assessment of effectiveness							
Investigator's Global Assessment (IGA)	X	X	X	X	X	X	x ¹³
Eczema Area and Severity Index (EASI)	X	Х	X	X	X	X	x ¹³
Scoring Atopic Dermatitis (SCORAD)	X	X	X	X	X	X	x ¹³
Pruritus numeric rating scale (NRS)	X	X	X	X	X	X	x ¹³
Dermatology quality of life index (DLQI)	X	X	X	X	X	X	x ¹³
Photography ⁵	X	X	X	X	X	X	x ¹³
safety assessment							
12-lead ECG	X	X	X	X	X	X	X

Vital signs (blood pressure, heart rate, temperature and respiratory rate) ⁶	X	х	X	X	X	X	Х
Adverse Event Assessment ⁷		X	X	X	X	X	X
Laboratory Evaluation							
Hematological and biochemical tests	X	X	X	X	X	X	х
Urinalysis	X	X	X	X	X	X	X
Lipid Profile (fasting)		X	X	X	X	X	X
TSH, fT3, fT4	X	X	X	X	X	X	X
QuantiFERON-TB Gold or T-SPOT.TB test	X						
Hepatitis B surface antigen, Hep C Ab, HIV test	X						
Immunoglobulin E (IgE)	X	X	X	X	X	X	x ¹³
Urine Pregnancy Test 8		X	X	X	X	X	X
β-HCG (blood) ⁹	X						
Medication							
Concomitant Medication Assessment	X	X	X	X	X	X	Х

- 1. Written informed consent must be obtained prior to performing any Visit 1 procedures or initiating any alterations in a subject's medications.
- 2. Atopic Dermatitis Disease History includes collection of details of AD: AD diagnosis, the use of topical treatments, systemic treatments and other treatments for AD.
- 3. Only to be performed if there is no chest X-ray or CT scan available within 3 months of Visit 1.
- 4. IVRS is a randomization system used to record all patient visits.
- 5. Subjects will be photographed at a distance of 1m by a fixed investigator at each visit (the principle of photography is to reflect the characteristics of AD skin lesion to the greatest extent). When photographed, face and private part will be well covered.

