g. All events of possible drug-induced liver injury with hyperbilirubinemia defined as ALT ≥ 3xULN and bilirubin≥ 2xULN (>35% direct) (or ALT≥ 3xULN and INR>1.5, if INR measured) termed 'Hy's Law' events (INR measurement is not required and the threshold value stated will not apply to patients receiving anticoagulants).

Note: bilirubin fractionation is performed if testing is available. If testing is unavailable, record presence of detectable urinary bilirubin on dipstick indicating direct bilirubin elevations and suggesting liver injury. If testing is unavailable and a subject meets the criterion of total bilirubin 2xULN, then the event is still reported as an SAE. If INR is obtained, include values on the SAE form. INR elevations >1.5 suggest severe liver injury.

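### The liver stopping rule in Protocol 7.3.8 includes an INR limb, but no visible section schedules or triggers an INR, and the limb lacks the anticoagulant exemption given in 7.3.12

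*Protocol*

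**What the plan says.** Protocol 7.3.8 lists four liver criteria, any of which requires immediate discontinuation: ALT or AST above 8x ULN; above 5x ULN and confirmed on retest; above 3x ULN with raised bilirubin or INR; and above 3x ULN with listed symptoms. The third reads "ALT or AST > 3 x ULN with elevated total bilirubin > 2 x ULN, or international normalized ratio > 1.5". Section 5.9 enforces the list: "Study treatment will be stopped if the liver chemistry stopping criteria is met".

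The laboratory plan is in two places. Table 1 in 5.11 has a row for "Hematological and biochemical tests" at every visit. Section 7.3.5 gives the analytes: "The study clinical laboratory tests including analytes for clinical chemistry and hematology are shown below in Table 6". Table 6 contains ALT, AST and bilirubin but no INR, prothrombin time or other coagulation test. The same section adds: "At the discretion of the investigator, additional samples may be taken for safety reasons".

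Once a criterion is met, 7.3.8 prescribes a work-up: "For one of above criteria, make every effort to carry out the liver event follow-up assessment of described below". It covers viral serology, a PK sample, CPK and LDH, bilirubin fractionation, blood count, symptoms, medications and alcohol. It does not include INR.

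The only other use of INR is in 7.3.12 item g, the Hy's Law SAE definition. There INR counts only where it has been measured, and the text adds: "INR measurement is not required and the threshold value stated will not apply to patients receiving anticoagulants". The note to that item says: "INR elevations >1.5 suggest severe liver injury".

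**The concern.** A mandatory safety rule should be executable from the plan that contains it. Here one limb depends on a value that sites are not told to obtain. The protocol itself treats an INR above 1.5 as a sign of severe liver injury, yet a site that follows the visible schedule exactly may never measure it.

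The limb can also mislead in the other direction. INR is raised on purpose by some anticoagulants. The authors allowed for this in the SAE definition but not in the stopping rule. A subject on such a drug, with a moderate enzyme rise, would have to leave treatment because of an INR that reflects the anticoagulant and not the liver.

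What is at stake is individual subject safety and avoidable discontinuation, not the efficacy inference.

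**Working it through.** The plan gives no figure to reproduce. The check is a comparison of sections, a run through the four criteria, and simple visit arithmetic.

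**Step 1. Where could an INR come from?**
- Table 1 (5.11): no visible INR or coagulation row.
- Table 6 (7.3.5): no INR.
- Visit 1 assessments (7.1) and early-withdrawal list (5.8): no INR.
- Work-up in 7.3.8: no INR. It also starts only after a criterion has been met, so it could not supply the value that the third criterion needs.
- Additional samples (7.3.5): possible, at the investigator's discretion. Nothing triggers one.

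**Step 2. When is INR the only 7.3.8 criterion that can be met?** Take a subject with none of the listed symptoms, so the fourth criterion is off.
- Enzyme above 8x: the first criterion stops drug without INR.
- Enzyme above 5x and up to 8x, bilirubin at or below 2x: the second criterion stops drug after the retest; until then only INR could.
- Enzyme above 3x and up to 5x, bilirubin above 2x: the bilirubin part of the third criterion stops drug.
- Enzyme above 3x and up to 5x, bilirubin at or below 2x: only INR can.

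**Step 3. Two illustrative subjects (values assumed).**
- Case A: ALT 4x, bilirubin 1.5x, INR 1.8, no symptoms. 4 > 8 is false; 4 > 5 is false; 4 > 3 is true, 1.5 > 2 is false, and 1.8 > 1.5 is true. The rule stops drug if INR is measured and does not if it is not.
- Case B: ALT 3.5x, bilirubin 0.9x, INR 2.5 on an anticoagulant. 3.5 > 3 is true and 2.5 > 1.5 is true, so 7.3.8 stops drug. Under 7.3.12 item g the INR threshold would not apply to this subject.

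**Step 4. Can Case B be enrolled?** Section 6.6.2 and Appendix 4 (CYP3A inhibitors and inducers) do not list anticoagulants. Section 6.6.4 bars only traditional Chinese or herbal products that increase bleeding. Inclusion criterion 6 accepts stable non-prohibited medication. The age limit is 75, and Appendix 3 excludes atrial fibrillation only with a ventricular rate above 100 bpm. So yes.

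**Step 5. Time to the next scheduled chemistry if Case A is missed.** Table 1 visits are days 7 ± 2, 28 ± 3, 56 ± 3 and 84 ± 3.
- Week 1 to Week 4: 28 − 7 = 21 days; range 25 − 9 = 16 to 31 − 5 = 26.
- Week 4 to Week 8, and Week 8 to Week 12: 28 days; range 28 − 6 = 22 to 28 + 6 = 34.

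With once-daily dosing, the longer interval is about 28 further doses if nobody retests. That is a worst case.

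**The case against.** The strongest reply is that INR was meant to be optional. Item g makes it so, ALT, AST and bilirubin are measured at every visit, and three of the four criteria, plus the bilirubin part of the third, work without INR. Subjects with ALT, AST or bilirubin above 2x ULN at screening are excluded, so few should reach the affected range. Case B errs toward caution, since the subject already has enzymes above 3x ULN. All of this stands and keeps the point small. It does not make the limb executable, because 7.3.8 carries neither the condition nor the exemption.

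Several stronger readings are tempting, and the documents do not support them.
- A reader might infer that Case A can be stopped only through INR. That is true only within 7.3.8. Section 5.9 also stops for an adverse event judged unacceptable, 7.3.11 counts abnormal laboratory findings as adverse events, and 5.8 lets the investigator discontinue a subject at any time.
- A reader might infer that item g contradicts 7.3.8. Its statement that INR is not required belongs to SAE reporting. The gap in 7.3.8 is shown by the laboratory plan alone; item g shows only that the authors recognised the anticoagulant problem.
- A reader might infer four weeks of unmonitored dosing. Section 5.6 asks for clinically significant abnormal values to be followed to normal or baseline, although it names no interval and no INR.
- A reader might infer that the hepatic rows in SAP 15.3 are defective for lacking INR. They do not claim to mirror 7.3.8, and also leave out the symptom criterion and the retest.

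**Conclusion.** The point holds at the low end of minor. The INR limb is mandatory on paper, but in practice it depends on a discretionary test. It is the only 7.3.8 criterion available in one narrow range: above 3x and up to 5x ULN, bilirubin at or below 2x ULN, no listed symptoms. The missing exemption is a separate, equally narrow gap. The documents give no frequency for either situation; few cases are expected. The primary endpoint, power and alpha are not affected.

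The conclusion rests on two readings. First, INR above 1.5 is taken to apply together with ALT or AST above 3x ULN. The punctuation could suggest INR alone, but item g supports the combined reading. Second, no INR is assumed to sit in the parts of the schedule that cannot be seen: Table 1 footnotes 10 and 11 are not visible, and the Study Procedures Manual is not available. Table 6 is legible and has no coagulation test, so a hidden INR is unlikely but cannot be ruled out.

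**What to change.** In Protocol 7.3.8:
- require a reflex INR whenever ALT or AST exceeds 3x ULN, and list it in Table 6 as a conditional test;
- state that the INR threshold does not apply to subjects receiving anticoagulants, and that all other liver criteria still do.

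If the sponsor prefers to keep INR optional, the minimum is to mark the limb as applying only where INR has been measured and to add the exemption. That makes the text consistent but leaves the range in Step 2 to discretion. No SAP change is needed.

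The cost is one additional blood assay in the few subjects above 3x ULN, and short wording changes in 7.3.8 and Table 6.
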